**Clinical Study Protocol**  
**Zr-TLX250-003**

Version: 8.0  
 Date: 01-Apr-2022

**Clinical Study Protocol**  
**Zr-TLX250-003**

Version: 8.0  
Date: 01-Apr-2022

## Study Synopsis

Study title	A confirmatory, prospective, open-label, multi-centre phase 3 study to evaluate diagnostic performance of  Zirconium-labelled girentuximab (  Zr-TLX250) to non-invasively detect clear cell renal cell carcinoma (ccRCC) by positron emission tomography/CT (PET/CT) imaging in patients with indeterminate renal masses (ZIRCON study)
Short title	 Zr-TLX250 for PET/CT imaging of ccRCC
Clinical study phase	3
Study objective(s)	
Primary objective
 
 
1. To evaluate sensitivity and specificity of qualitative assessment of PET/CT imaging with Zr-TLX250 to non-invasively detect ccRCC in patients with indeterminate renal masses, using histology as standard of truth.
 
 
Secondary objectives
 
Key secondary objectives of this study will be:
 
 
1. To determine sensitivity of Zr-TLX250 PET/CT imaging to detect ccRCC in the subgroup of patients with indeterminate renal masses of ≤ 4 cm in largest diameter (cT1a)
 
2. To determine specificity of Zr-TLX250 PET/CT imaging to detect ccRCC in the subgroup of patients with indeterminate renal masses of ≤ 4 cm in largest diameter (cT1a)
 
 
Other secondary objectives of this study will be:
 
 
3. To determine positive predictive value (PPV), negative predictive value (NPV), and accuracy of Zr-TLX250 PET/CT imaging to detect ccRCC in patients with
 

## Clinical Study Protocol

**Zr-TLX250-003**

Version: 8.0

Date: 01-Apr-2022

	
indeterminate solid renal masses, and in patients with indeterminate renal masses of <math>\leq 4</math> cm (cT1a)
 
 
4. To identify a standardized uptake value (SUV) cut-off for Zr-TLX250, suitable to discriminate ccRCC from non-ccRCC
 
5. To determine inter-reader variability of diagnostic assessments of Zr-TLX250 PET/CT images, when performed by multiple readers
 
6. To determine intra-reader variability of diagnostic assessment of Zr-TLX250 PET/CT images
 
7. To establish safety and tolerability of Zr-TLX250 in patients with indeterminate renal masses.
 
8. To evaluate sensitivity and specificity of Zr-TLX250 PET/CT imaging to detect ccRCC in patients with IRMs <math>\leq 3</math> cm, IRMs <math>\leq 2</math> cm, and Bosniak 3 and 4 lesions
 
 
Exploratory objectives
 
 
1. To quantitatively estimate achievable tumour uptake, retention and radiation absorbed doses (Gy) for therapeutic Lu-girentuximab, based on single time point Zr-girentuximab PET/CT images, a general model of average girentuximab tumour kinetics, derived from serial Zr-girentuximab imaging, and an assumed specific activity of Lu-girentuximab.
 
2. To evaluate the correlation between Zr-TLX250 SUVs and degree of histological CAIX expression.
 
3. To evaluate distant masses outside the kidney identified on Zr-TLX250 whole body PET/CT in patients who present with unexpected evidence of disseminated disease
 

Project code	Zr-TLX250-003
Investigational medicinal product (IMP)	 Zr-TLX250, a chimeric monoclonal antibody (INN name: girentuximab (GTX), synonyms: cG250, TLX250) with specificity for the CAIX (carbonic anhydrase 9) antigen, radiolabelled with the positron emitting radio-metal zirconium-89 via a NSuc-DFO-TFP-ester (DFO-TFP), linked to lysine residues of GTX, to yield  Zr-DFO-TFP-GTX.
Name of active ingredients	 Zr-TLX250 (synonyms:  Zr-girentuximab,  Zr-DFO-TFP-GTX)
Doses	A single administration of 37 MBq ( $\pm 10\%$ )  Zr-TLX250, containing a mass dose of 10 mg of girentuximab.
Route of administration	Slow intravenous administration (IV)
Duration of treatment	Single diagnostic administration, followed by a diagnostic scan on Day 5 $\pm$ 2 days
Reference product (RP)	Not applicable

## Clinical Study Protocol

Zr-TLX250-003

Version: 8.0

Date: 01-Apr-2022

Indication	 Zr-TLX250 is being developed as a PET/CT imaging agent for the characterisation, as ccRCC or non-ccRCC, of indeterminate renal masses (IRM).
Diagnosis and main criteria for inclusion	
All patients must meet all of the following criteria:
 
 
1. Written and voluntarily given informed consent
 
2. Male or female <math>\geq</math> 18 years of age
 
3. Imaging evidence of a single indeterminate renal mass of <math>\leq</math> 7 cm in largest diameter (tumour stage cT1) on standard of care imaging, based on national standards, not older than 90 days on Day 0, but performed before any screening procedure.
 
4. Scheduled for lesion resection as part of regular diagnostic work-up within 90 days from planned Zr-TLX250 administration.
 
5. Negative serum pregnancy tests in female patients of childbearing potential at screening. Confirmation of negative pregnancy test result from urine within 24 hours prior to receiving investigational product.
 
6. For patients included in France only, verification and confirmation of their affiliation with a social security
 
7. Sufficient life expectancy to justify nephrectomy.
 
8. Consent to practise highly effective contraception until a minimum of 42 days after Zr-TLX250 administration.
 

Exclusion Criteria	
A patient will be excluded from participation in the trial if one or more of the following criteria are met:
 
 
1. A biopsy procedure only (rather than partial or total nephrectomy) planned for histological species delineation of IRM
 
2. Renal mass known to be a metastasis of another primary tumour.
 
3. Active non-renal malignancy requiring therapy during the time frame of the study participation.
 
4. Chemotherapy, radiotherapy, or immunotherapy within 4 weeks prior to the planned administration of Zr -TLX250 or continuing adverse effects (> grade 1) from such therapy (Common Terminology Criteria for Adverse Events [CTCAE] version 5.0).
 
5. Planned antineoplastic therapies (for the period between administration of Zr-TLX250 and imaging).
 
6. Exposure to murine or chimeric antibodies within the last 5 years.
 
7. Previous administration of any radionuclide within 10 half-lives of the same
 
8. Serious non-malignant disease (e.g. psychiatric, infectious, autoimmune or metabolic), that may interfere with the objectives of the study or with the safety or compliance of the subject, as judged by the investigator
 
9. Mental impairment that may compromise the ability to give informed consent and comply with the requirements of the study.
 
10. Exposure to any experimental diagnostic or therapeutic drug within 30 days from the date of planned administration of Zr-TLX250
 

**Clinical Study Protocol**  
**Zr-TLX250-003**

Version: 8.0  
Date: 01-Apr-2022

	
11. Women who are pregnant or breastfeeding.
 
12. Known hypersensitivity to girentuximab or DFO (desferoxamine)
 
13. Renal insufficiency with GFR <math>\leq</math> 45 mL/min/ 1.73 m^2
 
14. Vulnerable patients (e.g. being in detention)


Study design
	
This will be a confirmatory, prospective, open-label, multi-centre phase 3 study to evaluate sensitivity and specificity of Zr-TLX250 PET/CT imaging to non-invasively detect clear cell renal cell cancer (ccRCC) in adult patients with indeterminate renal masses (IRM), scheduled for partial or total nephrectomy.
 
Histological confirmation will serve as standard of truth, to assess sensitivity, specificity, positive predictive value (PPV), negative predictive value (NPV), as well as accuracy of Zr-TLX250 PET/CT imaging.
 
According to current clinical practice in most specialist centres, patients with an IRM of <math>\leq</math> 7 cm in largest diameter (stage cT1, encompassing the subgroups cT1a <math>\leq</math> 4 cm, and cT1b <math>></math> 4 cm to <math>\leq</math> 7cm), restricted to the kidneys are routinely subjected to partial or total nephrectomy, as this intervention has curative potential in most cases.
 
For that reason this study will be conducted in patients with IRM of stage cT1, and histological material will be obtained as part of routine nephrectomy, circumventing the need for study-specific invasive procedures. Given a reported high rate of non-diagnostic kidney biopsies, patients scheduled to undergo kidney biopsy only, rather than nephrectomy are not eligible for this study.
 
The proportion of patients with a stage cT1 IRM, who actually do not have ccRCC (non-ccRCC patients, i.e. those in whom following surgical removal, ccRCC can be histologically ruled out) has been reported to range between 20–40%. This proportion appears to be higher in smaller (cT1a), compared with larger (cT1b) lesions.
 
For a total study population of cT1 patients composed of 70% of the cT1a subgroup (IRM <math>\leq</math> 4 cm), and assuming 34% non-ccRCC in the cT1a subgroup, a total sample size of 252 patients provides 90% power to confirm both a sensitivity and specificity of 83%, as previously reported for cT1a lesions for prior GTX-based imaging agents (I-girentuximab, In-girentuximab). The total sample size of 252 gives 90% power to distinguish a 68% specificity threshold, assuming a non-ccRCC rate in the cT1b subset of at least 17%.
 
In order to ensure that a sufficient number of patients with cT1a tumour stage and sufficient patients with non-ccRCC histopathology will be included into the total study population, patient accrual and histological results will be centrally evaluated and monitored by an Independent Data Monitoring Committee (IDMC); recruitment into the study will continue until the minimum required number of patients has been recruited. The IDMC members will not have access to Zr-TLX250 PET/CT images, nor will they have access to the PET/CT results from the independent image reviewers.


## Clinical Study Protocol

### Zr-TLX250-003

Version: 8.0  
Date: 01-Apr-2022

Patients who are enrolled, but are then either not administered with study drug, or who do not undergo PET/CT imaging after administration of study drug, in whom PET/CT images can not be analysed due to technical failure, or in whom surgical material can not be assessed for presence or absence of ccRCC, are defined as drop-outs. Drop-out patients will be replaced for the primary analysis and study sample size. Missing data are not expected for efficacy outcomes involving the standard of truth (i.e., sensitivity, specificity, PPV, NPV, accuracy, inter-reader and intra-reader variability).

Patients will be recruited in 35–40 renal cancer care specialist centres, who have access to state-of-the-art PET/CT imaging.

Following informed consent, a screening visit will be performed during which baseline examinations will be made. The study schedule will be planned considering a delivery timeline for Zr-TLX250 of 7 – 10 days from the central study radiopharmacy, the day of administration, a PET/CT scan of the kidneys at 5 ± 2 days post administration, and the nephrectomy to be performed any time after the PET/CT imaging visit, but no later than 90 days post administration of Zr-TLX250.

On Day 0, all successfully screened patients will undergo a slow intravenous administration over a minimum of 3 minutes with Zr-girentuximab, at the nuclear medicine service of the respective study site. Before and after administration, safety evaluations will be made.

Female patients of childbearing potential will need to have their negative pregnancy test result from screening confirmed by a negative urine pregnancy test performed within 24 hours prior to dosing.

Patients, in whom unexpected evidence for disseminated disease is observed, PET/CT imaging may be extended to whole body imaging (skull base to mid-thigh) at the discretion of the investigator. Patients will be informed as part of the consent procedure that any PET imaging result will not be disclosed to them until the scheduled nephrectomy has actually been performed or until surgery has been cancelled in case metastatic disease going beyond the kidney is present.

A histological tumour sample from nephrectomy (15 paraffin embedded slides) will be prepared by the local institutional pathology service, and sent to the central laboratory which will determine the histological diagnosis of the renal mass – the standard of truth - (ccRCC or non-ccRCC), and determine the degree of CAIX expression. For patients in whom unexpected evidence of disseminated disease is observed, any available tissue samples from biopsies of extrarenal lesions will also be analysed centrally.

On Day 42 ± 7 days p.a., a visit will be performed for all patients, during which the potential formation of anti-drug antibodies (HACA) and safety parameters will be investigated.

At the final study visit, testing for HACA will be repeated, where feasible, and all necessary safety assessment will be performed. For patients who were nephrectomised within 28 days p.a., the final

**Clinical Study Protocol**  
**Zr-TLX250-003**

Version: 8.0  
Date: 01-Apr-2022

	
study visit will be conducted on Day 42 (<math>\pm</math> 7 days). For patients with nephrectomy between 28 and 90 days p.a., the final study visit will be performed 35 days (<math>\pm</math> 7 days) after surgery.
 
Image data analyses will be performed by a central image core lab. Qualitative visual analysis (presence or absence of localised Zr-TLX250 uptake inside or in vicinity of renal lesion, as seen on contrast-enhanced pre-BL MRI or equivalent standard of care imaging with contrast agent), will be used to assess test performance of Zr-TLX250 PET/CT imaging to detect ccRCC, using histological results from the central histological reference laboratory as standard of truth.
 
Lesions of interest will be spatially localised by the site, and independently by the image readers. The readers of the central lab will not have access to the spatial localisation determined by the site.
 
Reading of the images will be conducted centrally and independently by three trained readers, blinded to patient medical history and any previous histology results.
 
Zr-TLX250 SUVs will be determined for each tumour lesion. Receiver operating characteristics (ROC) will be analysed to identify a SUV cut-off value, most appropriate to discriminate between ccRCC or non-ccRCC (ccRCCnegative) as evidenced by central histology results.
 
Zr-TLX250 activity and antibody mass concentrations in tumour at the time of imaging (MBq/cm^3, mg/cm^3) will be determined, considering the absolute activity bound to the tumour, lesion volume as determined by CT/MRI, and the decay-corrected specific activity.
 
Image-derived non-primary variables will be exploratively compared to histological and clinical parameters, where merited.


Study Participation Duration
	
 
• Screening period: 30 days (Day -30 to Day -1)
 
• Experimental part of the study: 
 
- Treatment: IMP administered on Day 0
 
- Imaging visit: Day 5 <math>\pm</math> 2 days
 
- Surgery: any time after imaging visit, but no later than Day 90 p.a.
 
 
 
• Day 42 <math>\pm</math> 7 days p.a., HACA testing
 
• Final study evaluation 
 
- HACA testing and safety assessments: either Day 42 p.a., or 35 <math>\pm</math> 7 days after nephrectomy, depending on day of surgery
 
 
 

Methodology
	
Pre-screen morphological image for identification of an indeterminate solid renal mass
 
Availability of a recent contrast-enhanced abdominal MRI or equivalent imaging modality with contrast agent as part of standard of care, not older than 90 days on Day 0, but before any screening procedure, providing evidence of a newly diagnosed, single renal mass, confined to the kidney, and

measuring  $\leq 7$  cm in greatest diameter (stage cT1) (inclusion criterion).

Pre-BL contrast-enhanced images will be collected for precise volumetric tumour delineation, since in the context of the study, no contrast-enhanced CT or MRI will be performed.

### **Zr-TLX250 PET/CT imaging**

#### **1. PET imaging**

Abdominal PET/CT scans including the kidneys will be acquired over 20 minutes in a single bed position if possible at a single time point on Day 5  $\pm$  2 post administration (p.a.) of Zr-TLX250 using static image acquisition and low dose CT.

Patients found to have evidence of N1 or M1 disease may undergo additional whole body PET/CT imaging (skull base to mid-thigh) using 6-8 bed positions with 10 minutes acquisition time per bed position at the discretion of the treating clinician to support comprehensive staging. The additional scan if requested by the treating physician needs to be completed on Day 5  $\pm$  2 post administration of the investigational product.

#### **2. Qualitative Zr-TLX250 tumour targeting**

Zr-TLX250 tumour uptake will qualitatively be assessed (yes / no), considering whether or not Zr-TLX250 binding inside or in the vicinity of the target lesion, as delineated on structural imaging (contrast-enhanced pre-BL imaging), can be detected.

#### **3. Quantitative Zr-TLX250 tumour targeting**

Absolute activity concentrations of tracer in tumour (MBq/cm^3) will be calculated using attenuation-corrected count rates, and tumour volumes, as determined by contrast-enhanced pre-BL imaging. Considering specific activity (MBq/mg), protein mass dose concentrations of tracer in tumour at the time point of imaging (mg/cm^3) will be calculated.

#### **4. Estimation of Lu-girentuximab tumour targeting**

Protein mass dose concentrations of tracer in tumour (mg/cm^3) at the single time point of imaging, and a general model of average girentuximab kinetics in tumour over time (derived from sequential Zr-TLX250 biodistribution data), will be used, to estimate possible girentuximab protein kinetics in tumour lesions over a period of one week, assuming the kinetics of diagnostic Zr-TLX250 and therapeutic Lu-girentuximab are essentially similar. Such protein kinetic data can be used, to generate simulated time-activity curves for Lu-girentuximab in tumour for different specific activity levels, to yield estimates of achievable therapeutic absorbed doses to tumour (Gy).

### **Determination of histological standard of truth**

Surgical resection material, along with appropriate documentation of its in situ origin (to allow identification with lesion localisation on PET images) will be sent to local pathology for routine histological

**Clinical Study Protocol**  
**Zr-TLX250-003**

Version: 8.0  
 Date: 01-Apr-2022

	
work-up (H&E staining, histological diagnosis: ccRCC vs. non-ccRCC).
 
In addition, non-stained slides of the indeterminate mass removed during surgery will be sent to a central histology lab, for independent determination of histological diagnosis and detection of CAIX.
 
In addition, where available, histological diagnosis of ccRCC and the detection of CAIX will be conducted on available tissue samples from biopsies of extrarenal lesions from patients in whom unexpected evidence of disseminated disease has been observed.
 
Diagnostic performance
 
Test performance parameters (sensitivity, specificity, positive and negative predictive values, accuracy), will be determined considering visually determined qualitative Zr-TLX250 tumour uptake (yes/no), and histology (ccRCC+/ ccRCC-) as standard of truth.
 
Safety
 
The following safety evaluations will be made:
 
 
1. Standard laboratory (haematology, biochemistry)
 
2. Adverse event recording (NCI-CTC v 5.0)
 
3. Concomitant medication recording
 
4. 12-lead ECG
 
5. Vital signs
 
6. HACA (human anti-chimeric antibodies)
 
								
Type of control	Not applicable								
Planned study dates	
 
 Start of study recruitment	Q1/2019	End of recruitment	Q3/2022	
 
 		End of study	Q4/2022	
 
	Start of study recruitment	Q1/2019	End of recruitment	Q3/2022			End of study	Q4/2022
Start of study recruitment	Q1/2019	End of recruitment	Q3/2022						
		End of study	Q4/2022						
Planned number of study centres/countries	35-40 centres in the EU (Belgium, France, Spain, the Netherlands), UK, Turkey, Australia, Canada and USA.								

**Clinical Study Protocol**  
**Zr-TLX250-003**

Version: 8.0  
Date: 01-Apr-2022

Number of patients	
Total: approximately 252 patients scheduled for partial or total nephrectomy
 
Sample Size: The total number of patients expected to be enrolled is n=252: it is expected that these will include 194 patients with cT1a tumours and 58 patients with cT1b tumours With 194 patients with cT1a tumours it is expected that these will include at least the required number of 128 patients that are ccRCC positive and 66 patients that are ccRCC negative. Based on the actual number of patients observed during trial enrolment with cT1a tumours that are ccRCC positive and ccRCC negative, the total sample size might need to be increased to ensure the minimum of at least 128 and 66, respectively. Therefore, the distribution of enrolled patients will be centrally monitored (reviewing of staging and histology (without imaging results)).
									
Co-primary variables	
Sensitivity and Specificity of Zr-TLX250 PET/CT imaging to detect ccRCC
 
These will be determined, considering the histological diagnosis (ccRCC+ or ccRCC-) as determined by the central study pathology as standard of truth, and the qualitative Zr-TLX250 tumour targeting (tracer uptake in target lesion: yes/no), as determined by visual reading, to yield a 2 x 2 table as follows:
 
  
 	ccRCC+	ccRCC-	
   
 PET+	TP	FP	
 
 PET-	FN	TN	
  
 
Abbreviations: FN=false negative; FP=false positive; TN=true negative; TP=true positive
 
a) Sensitivity will be the proportion of study patients with a true positive (TP) PET scan, out of those with positive histology for ccRCC Sensitivity (%) = TP / (TP + FN)
 
b) Specificity will be the proportion of study subjects with a true negative (TN) PET scan, out of those with negative histology for ccRCC Specificity (%) = TN / (TN + FP)
		ccRCC+	ccRCC-	PET+	TP	FP	PET-	FN	TN
	ccRCC+	ccRCC-								
PET+	TP	FP								
PET-	FN	TN								
Secondary variables	
Further test performance parameters
 
a) Positive predictive value (PPV) PPV (%) = TP / (TP + FP)
 
b) Negative predictive value (NPV) NPV (%) = TN / (TN + FN)
 
c) Accuracy Accuracy (%) = TP + TN / (TP + FP + TN + FN)
 
Standardised uptake value (SUV)
									

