#### 9.3.1 Sample Size Estimation

The study sample size for the population of patients with indeterminate renal mass (i.e., patients with cT1 tumors) has 2 components: Sensitivity and Specificity. Sample size is estimated for Sensitivity and Specificity, respectively, and the larger of the two estimates will represent the final study sample size. The basic assumptions underlying sample size estimation are the following:

- In the population of patients with indeterminate renal mass (i.e. cT1 patient population), approximately 70% are cT1a and 30% are cT1b patients.
- In the cT1a subpopulation, approximately a third (34%) are expected to show no signs of renal cell carcinoma following histopathology assessment (i.e. ccRCC negative).
- It is expected from a clinical standpoint that the subpopulation of cT1b patients would show a much lower rate of negative histopathologies than the cT1a subpopulation. For the purpose of powering this trial, it is assumed that the rate of non-ccRCC histopathologies in the cT1b subpopulation would be at least 17%, half the rate in the cT1a subpopulation.

**Sensitivity:** to ensure the study has 90% power to show that the lower limit of the 2-sided 95% confidence interval (Wilson) for sensitivity is above the critical limit (or non-inferiority limit) of 70%, the minimum sample size required for the population of cT1 patients under above assumptions is 125, when assuming a true sensitivity of 83%.

**Specificity:** to ensure the study has 90% power to show that the lower limit of the 2-sided 95% confidence interval (Wilson) for the specificity is above the critical limit (or non-inferiority limit) of 68%, the minimum sample size required for the population of cT1 patients under above assumptions is 252, when assuming a true specificity of 83%.

An estimated total of 252 patients with an IRM of  $\leq 7$  cm and scheduled partial or radical nephrectomy will be included in the study. However, in order to maintain adequate study power, this number may be increased depending on the proportion of non-ccRCC patients after surgery and histological verification.

Table 6 provides an example of the expected sample size required with different observed non-ccRCC rates.

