### 9.3.2 Independent Data Monitoring Committee

An independent data monitoring committee (IDMC) will be established by the sponsor and will monitor the number of evaluable patients cT1a and cT1b tumors, and with ccRCCpositive ccRCCnegative tumors and give feedback to the sponsor on whether the planned sample size is appropriate or not.

The IDMC will evaluate patient accrual and histological results at 50% (126) and 75% (189) of evaluable cases. Counts of evaluable cases (excluding cases where Zr-TLX250 PET/CT imaging and/or tissue collection were either not performed or are pending) in 4 categories based on initial tumour size (cT1a, cT1b) and IRM histology (ccRCC, non-ccRCC). The IDMC will provide feedback to the sponsor of whether the proposed sample size will be likely to be sufficient or not. Based upon this feedback the sponsor may consider an amendment to the protocol that could modify inclusion criteria to include only cT1a patients subsequently or to increase the sample size to ensure sufficient power.

Enrollment will not be halted during the data review procedure.

The IDMC members will not review Zr-TLX250 PET/CT images or imaging data, nor will they have access to the results generated by either the independent image readers or the local reader.

The committee will be composed of at least three members, specialised in biostatistics, pathology and/or oncology. The committee will have the above described responsibility only that will be detailed in an IDMC charter.

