Following comments from FDA and considering the actual numbers of patients with cT1a tumours enrolled into the trial either, the total sample size was increased to allow a minimum number of ccRCC negative patients to ensure sufficient statistical power for the key secondary endpoint. The statistical sample size calculation triggered a slight change to the definition of the statistical power adaptation of patient recruitment.

Table 2 provides an example of the expected sample size required with different observed non-ccRCC rates.

Table 2: Planned sample size estimates*

	Outcome	Null	Alt.	Non-ccRCC Rate in CT1a Group	Non-ccRCC Rate in CT1b Group	Alpha	Power	N Total
Scenario (1)	Specificity	0.68	0.83	0.34	0.17	0.05	0.90	252
	Sensitivity	0.70	0.83	0.34	0.17	0.05	0.90	125
Scenario (2)	Specificity	0.68	0.83	0.25	0.20	0.05	0.90	284
	Sensitivity	0.70	0.83	0.25	0.20	0.05	0.90	116
Scenario (3)	Specificity	0.68	0.83	0.25	0.15	0.05	0.90	317
	Sensitivity	0.70	0.83	0.25	0.15	0.05	0.90	114

* Sample size estimates to achieve 90% power based on rates of non-ccRCC in both CT1a and CT1b groups. Scenario (1) represents the originally planned sample size; while Scenario (2) and Scenario (3) provide potential sample size updates based on different non-ccRCC rates.

Note that both sensitivity and specificity will be determined for each of three independent readers. The study will be successful if the lower bounds of the 95% confidence intervals (CIs) for sensitivity (>70%) and specificity (>68%) in at least the same 2 out of 3 independent readers.

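### The synopsis writes the expected split of 194 cT1a patients (128 ccRCC, 66 non-ccRCC) as two simultaneous minima, which 194 patients meet with only a 6% chance

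*Protocol*

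**What the plan says.** The protocol synopsis, under Number of patients, plans 252 patients: "it is expected that these will include 194 patients with cT1a tumours and 58 patients with cT1b tumours". The 194 are expected to contain "at least the required number of 128 patients that are ccRCC positive and 66 patients that are ccRCC negative". Depending on what is observed, "the total sample size might need to be increased to ensure the minimum of at least 128 and 66, respectively".

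Protocol section 9.3.1 supplies the assumptions. On the non-ccRCC rate: "In the cT1a subpopulation, approximately a third (34%) are expected to show no signs of renal cell carcinoma"; for cT1b the rate "would be at least 17%, half the rate in the cT1a subpopulation". The cT1a share is put at 70%. For sensitivity (83% against a limit of 70%, two-sided 95% Wilson interval, 90% power), "the minimum sample size required for the population of cT1 patients under above assumptions is 125, when assuming a true sensitivity of 83" percent. Specificity (83% against 68%) needs 252. The section gives no ccRCC-positive minimum and makes any increase depend on the non-ccRCC proportion. Section 4.2.3 says the same. The synopsis's own Study design entry speaks of securing enough cT1a patients and enough non-ccRCC patients.

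Section 9.3.2 sets the monitoring: "The IDMC will evaluate patient accrual and histological results at 50% (126) and 75% (189) of evaluable cases". It names four cells to be counted but no minimum for any of them. SAP section 7 reports that "the total sample size was increased to allow a minimum number of ccRCC negative patients", and SAP section 5.1 gives the raised enrolment as 300.

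**The concern.** Two minima that add up to exactly the planned number leave no room for chance. A patient above the minimum in one group is a patient below it in the other. So the statement that 194 cT1a patients are expected to contain at least both counts cannot describe what 194 patients will usually give.

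The two counts are also the only numeric criteria in the documents for deciding whether the cT1a sample is large enough. If one of them is just a remainder, the sponsor and the monitoring committee could be comparing accrual with a figure that no test needs. The synopsis would also be asking for something that the statistics section and the SAP do not ask for.

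**Working it through.** **Inputs.** 194 cT1a patients and the counts 128 and 66 (synopsis); 34% and 17% non-ccRCC, 70% cT1a share, sensitivity 83% vs 70%, specificity 83% vs 68%, 90% power, two-sided 5% (protocol 9.3.1); enrolment of 300 (SAP 5.1).

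**Where 66, 194 and 128 come from.** With the variance taken at the alternative, n = p1(1 − p1)(1.960 + 1.282)² / (p1 − p0)², where the squared term is 10.507.

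- Specificity: 0.83 × 0.17 × 10.507 / 0.15² = 65.9, so 66 non-ccRCC.
- 66 / 0.34 = 194.1, so 194 cT1a patients.
- 194 − 66 = 128 (equally, 194 × 0.66 = 128.04).

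This reproduces the synopsis figures. The 128 appears only as the remainder.

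**What the sensitivity test needs.**

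- Expected ccRCC share of all cT1: 1 − (0.70 × 0.34 + 0.30 × 0.17) = 0.711.
- The plan's own 125 patients therefore imply 125 × 0.711 = 88.9, about 89 ccRCC. The same formula gives 0.83 × 0.17 × 10.507 / 0.13² = 87.7, so 88.
- Under the written rule (lower Wilson 95% limit above 0.70), exact binomial power per reader at a true 83% is 83.0% at n = 89, first reaches 90% at n = 108 (90.3%), is 89.8% at n = 119, and never falls below 90% from n = 120 (92.7%) upward. At n = 128 it is 94.0%.

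None of these calculations gives 128.

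**Chance that 194 patients meet both minima.** Let X be the number of non-ccRCC among 194, binomial with rate 0.34. Both minima require X ≥ 66 and 194 − X ≥ 128, that is X = 66.

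- P(X = 66) = 6.0%.
- P(X ≤ 65) = 47.5%: the 66 is missed.
- P(X ≥ 67) = 46.4%: the 128 is missed.

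No other true rate raises the first figure above about 6.0%; it is 2.9% at 30% and 3.1% at 38%.

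**Cost of the 128.** When only the 128 is missed, the mean ccRCC count is 122.4. The mean shortfall is 128 − 122.4 = 5.6, and 5.6 / 0.66 = 8.5 further cT1a patients (simulation: mean 8.5, median 7, 90th percentile 17). Over all trials that start from 194, the simulated mean cT1a number is 201.8 to reach the 66 alone and 205.7 to reach both, so the 128 adds about 4.

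| cT1a patients | P(at least 66 non-ccRCC) | P(both minima) |
|---|---|---|
| 194 | 52.5% | 6.0% |
| 210 | 80.4% | 75.0% |
| 219 | 90.0% | 89.2% |
| 220 | 90.8% | 90.2% |

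At the SAP's 300, P(both) is about 69% with a 70% cT1a share and about 96% with the 77% share implied by 194/252.

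**What 66 delivers.** Under the Wilson rule for specificity, exact power per reader at 66 non-ccRCC (83% vs 68%) is 77.7%. It first reaches 90% at 86 and stays there from 94.

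**The case against.** The strongest case on the other side accepts the sum and the 6% but denies that much follows from them.

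- The text is permissive: the total might need to be increased, the committee only gives feedback, and the sponsor may then consider an amendment. No rule tests both counts at exactly 194. This stands. A reader might infer that the trigger fires in about 94% of trials; the documents describe no automatic trigger.
- The statistics section, the recruitment section and the SAP act on non-ccRCC patients only, so the 128 sits in one synopsis statement. This stands, and it is also the inconsistency to be removed.
- A reader might infer that enrolment to reach 128 is needless because the limiting non-ccRCC count is already met. The plan's own test does not support that. Meeting 66 leaves specificity power at about 78% per reader, and about a third of any added cT1a patients would be non-ccRCC, the group that is short.
- The claim that no calculation requires 128 rests on applying 0.70 vs 0.83 to cT1a, for which the plan states no threshold. If the synopsis's 90% power for both endpoints meant joint power, each would need about 95%, and the Wilson approximation then gives 136 ccRCC. The documents do not state that target, so this qualifies the point without explaining the 128.
- At 300 patients both minima become likely. This stands, but the synopsis still gives 194 and 252.

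**Conclusion.** An expected split has been written as a pair of minima. The planned 194 cT1a patients meet both with a 6.0% chance at the plan's own 34%, and the 128 follows from no sensitivity calculation that the documents state. The arithmetic needs only the 34% rate and 194 cT1a patients; it does not depend on whether the cT1a share is 70% or 77%. The comparison with sensitivity power also assumes that the cT1 thresholds carry over to cT1a.

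The consequence is modest: about 8 further cT1a patients on average when the 128 is the count missed, and one patient (220 against 219) at a 90% chance of success. The documents do not support reading this as forced or wasted enrolment. It is a wording and consistency defect in the recruitment criterion, cheap to correct, and the correction should not endorse 66 as sufficient for 90% power.

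**What to change.** In the synopsis entry on number of patients:

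1. Describe 128/66 as the expected split of 194 cT1a patients at 34%, and drop 128 as a reason to raise the total, in line with protocol section 9.3.1 and SAP section 7.
2. State that 194 cT1a patients give about a 52% chance of at least 66 non-ccRCC, and that about 219 give a 90% chance.
3. Do not present 66 as giving 90% power. Either report what it delivers under the Wilson rule (about 78% per reader, 83% vs 68%), or derive the floors for both groups by the same exact Wilson calculation: about 120 ccRCC and 94 non-ccRCC for power held at 90%. State the cT1a thresholds on which this rests.
4. Reconcile the synopsis figures of 194 and 252 with the SAP's 300.

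Items 1, 2 and 4, and the first option in item 3, are changes of text and need no patients; the stated expectation for 194 becomes less favourable. The second option in item 3 has a real cost: 94 / 0.34 = 276 cT1a patients in expectation, against 300 × 0.70 = 210 to 300 × 0.77 = 231 at the SAP's enrolment.
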